6.8.2 Grip Strength Measurement

At baseline, and 12 weeks, and 52 weeks, the study coordinator will measure the patients' grip strength using the Smedley Dynamometer. The study coordinator will be trained on using the dynamometer. They will be instructed to take 3 consecutive grip strength measurements on each hand, and they will use and record the highest result for each hand.

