2.3 Exploratory Objective

- 2.3.1 To study whether grip strength may serve as an accurate and reliable objective measure to complement the subjective complaint of AIA.
- 2.3.2 To investigate whether high dose vitamin D may be associated with lower breast cancer recurrence than standard dose Vitamin D

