10. CORRELATIVE/SPECIAL STUDIES

10.1 Grip Strength

To further investigate whether grip strength may serve as a simple, objective measure of AIA, we will measure grip strength at baseline, week 12 and week 52 visits (see study Calendar in Appendix B), and see whether changes in grip strength do correlate with changes in joint pain, as represented in the HAQ score. Research coordinators will measure grip strength as outlined in [Section 6.8.2](#).

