AIA because the questionnaire has been validated through many other studies which examine joint pain, and it is very simple to do in the office in less than 5 minutes. Though grip strength will be measured at various time points throughout the study, it will only be used in the exploratory analysis to see whether it may be an appropriate measure for AIA. Grip strength measurement is a relatively easy, inexpensive, objective criteria which may help to more clearly define AIA. This data will be very useful in the future, as it may serve to support a clearer, more objective definition of AIA for use in future studies, and for use in clinical practice.

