13.6 Exploratory Endpoints

For each patient on the study, grip strength will be correlated with AIA score using logistic regression analysis and Spearman correlation at three time points throughout the study – baseline, week 12, and week 52. At five years, we will also compare breast cancer recurrence rates in each arm using Kaplan-Meier survival analysis and log-rank test.

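### Only the highest of three grip readings per hand is recorded, so within-session repeatability cannot be estimated although objective 2.3.1 asks whether grip strength is reliable

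*Combined protocol and SAP*

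**What the plan says.** Objective 2.3.1 is "To study whether grip strength may serve as an accurate and reliable objective measure to complement the subjective complaint of AIA".

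Section 6.8.2 sets the schedule: "At baseline, and 12 weeks, and 52 weeks, the study coordinator will measure the patients' grip strength using the Smedley Dynamometer". At each of these sessions staff are to "take 3 consecutive grip strength measurements on each hand, and they will use and record the highest result for each hand". Nothing in the protocol or the study calendar says that the other two readings are kept.

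Two sections describe the use of the data. Section 10.1 will "see whether changes in grip strength do correlate with changes in joint pain, as represented in the HAQ score". Section 13.6 states that "grip strength will be correlated with AIA score using logistic regression analysis and Spearman correlation at three time points throughout the study". Neither includes a repeatability statistic. Section 12.2 limits the role of grip strength: "it will only be used in the exploratory analysis to see whether it may be an appropriate measure for AIA".

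**The concern.** Association with HAQ-II tells us whether grip strength follows the complaint it is meant to complement. It does not tell us how far two readings on the same hand in the same session differ by chance. Estimating that needs repeat readings. The trial takes them, and the recording rule then drops two of every three.

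At stake is one component of an exploratory objective. Section 12.2 hopes that the grip data will support a more objective definition of AIA in later studies and in practice. Any threshold for a meaningful loss of grip would need a figure for measurement error. The same section gives HAQ-II a minimal important difference of 0.2; grip strength would leave the trial with no error figure. Readings that are not written down at the visit cannot be recovered.

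**Working it through.** The documents give no figure for grip strength, so there is no stated number to reproduce. There are two checks.

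**1. What the recorded data can estimate**

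- Inputs from 6.8.2: three readings per hand, two hands, three sessions, one value recorded per hand per session.
- Degrees of freedom for within-session error, per hand per session, are the readings recorded minus 1. As written: 1 − 1 = 0. With all three kept: 3 − 1 = 2.
- Per woman per visit with all three kept: 2 × 2 hands = 4. At baseline, with the 186 women of Section 13.2: 186 × 4 = 744. For independent normal errors the relative standard error of the within-woman SD is about 1/√(2 × 744) = 2.6%. The missing quantity would therefore be well estimated from baseline alone.
- The other recorded values are no substitute. The two hands can truly differ. Values at baseline, week 12 and week 52 mix measurement error with real change on AI therapy.

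**2. Whether the highest is a noisier summary than the mean**

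Assumptions: independent reading errors with single-reading variance 1. The documents give neither the size nor the shape of the error, so several shapes were tried with 2,000,000 simulated triples each. The mean of three has variance 1/3 = 0.33 for every shape.

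| Error shape | Variance of the highest of three | Variance of the mean |
|---|---|---|
| Normal | 0.56 | 0.33 |
| Uniform | 0.45 | 0.33 |
| Right-skewed (exponential) | 1.36 | 0.33 |
| Left-skewed (gamma, shape 4) | 0.27 | 0.33 |
| Left-skewed (gamma, shape 2) | 0.19 | 0.33 |
| Left-skewed (exponential) | 0.11 | 0.33 |

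The exponential rows can be checked by hand. Left-skewed: the highest reading corresponds to the smallest of three exponential shortfalls, with variance 1/3² = 0.11. Right-skewed: 1 + 1/4 + 1/9 = 1.36.

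Effect on a correlation with HAQ, normal errors only: reliability = 1/(1 + v(1 − ICC)/ICC), where ICC is the single-reading value (assumed range 0.70 to 0.95) and v is 0.5595 for the highest or 1/3 for the mean. The observed correlation scales with the square root of reliability.

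| Assumed ICC | Highest | Mean | Loss in correlation with the highest |
|---|---|---|---|
| 0.70 | 0.807 | 0.875 | 1 − √(0.807/0.875) = 4.0% |
| 0.80 | 0.877 | 0.923 | 2.5% |
| 0.90 | 0.942 | 0.964 | 1.2% |
| 0.95 | 0.971 | 0.983 | 0.6% |

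These losses are for values at a single visit. For changes between visits, as in 10.1, error enters twice and the loss under normal errors would be larger. Its size depends on the variance of true change and on between-session error. The documents give neither, so no figure is put on it.

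**The case against.** The strongest reply is that the word reliable in 2.3.1 need not carry its psychometric meaning. Sections 10.1 and 12.2 explain what the protocol wants to know: whether grip strength is a simple, objective and appropriate measure of AIA, judged against HAQ. Section 13.6 plans that analysis and the recorded data allow it. On this view only an extra statistic is missing, one that the plan never promised. This stands in part. A reader might infer that reliability cannot be assessed at all, or that the objective cannot be answered. The documents do not support that: the association can be analysed, and rough long-interval stability could be examined in women whose HAQ has not changed. What cannot be obtained is same-session repeatability.

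A reader might also infer that recording the highest is a poor choice of summary because a maximum is noisier than a mean. That is not established. Grip is a best-effort test, so errors that are mostly shortfalls from full effort are plausible, and for those the highest is the less noisy summary. Nothing in the documents settles the shape.

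Finally, three consecutive squeezes in one session show within-session error only. They say nothing about day-to-day or between-rater reliability across up to five centers. If grip change and HAQ change correlate weakly, the extra readings would show how much within-session error contributes. They could not separate out between-session error in grip or error in HAQ itself. This stands and limits the gain.

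**Conclusion.** The point holds in a narrow form. As Section 6.8.2 is written, within-session repeatability and measurement error of grip strength cannot be estimated, although 2.3.1 asks about reliability and the readings needed are already taken. This follows from the recording rule and needs no assumption beyond the documents.

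The choice of the highest as the analysis value is not an error. Whether it is noisier or less noisy than the mean depends on an unknown error shape. Even under independent normal errors the loss in a single-visit correlation is about 0.6% to 4% over assumed ICCs of 0.95 to 0.70.

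Impact is low. Grip strength is exploratory and is not part of the AIA definition. The primary test and the sample size are unaffected. This is a cheap improvement and not a correction that the trial depends on.

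**What to change.** - Section 6.8.2: require all three readings for each hand to be recorded, in the order taken, and state that the highest remains the planned analysis value.
- Section 13.6: add a within-session intraclass correlation and within-woman SD for each hand, and repeat the grip analyses with the mean of three as a sensitivity summary. The pooled readings would also show the error shape, and so which summary is less noisy in this population.
- State in 13.6 that these figures describe within-session error only.

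Cost: six values per grip visit in place of two, so four more per visit and 4 × 3 = 12 more per woman over the three scheduled sessions, plus the added text in 13.6. No new procedure, visit or staff is needed.

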6.8.3 Compliance with AI therapy

Compliance with aromatase inhibitor therapy will be evaluated by a physical pill count at the scheduled clinic visits on Weeks 12, 24, 36, and 52. Subjects will be instructed to bring their used bottles of aromatase inhibitor to each return visit, along with any unused tablets. Study staff will count the number of remaining tablets at each visit to assess compliance. In the event that the subject forgets to bring their used study meds to their clinic visit, compliance will be assessed by direct questioning of the subject. In this case, subjects should be counseled to bring their used drug bottles to their next scheduled clinic appointment so that compliance may be confirmed by pill count. Subjects should be instructed to report any missed doses of aromatase inhibitor to the study coordinator.

Compliance with the aromatase inhibitor will be calculated by the ratio of number of pills actually taken to the number of pills that should have been taken. Compliance will be defined as a ratio ≥ 0.80 . Study staff should ensure subject understanding of dosing instructions for subjects whose compliance is less than 100%. In addition, the importance of compliance with anticancer therapy should be reinforced. In the case of non-compliance, the study coordinator will ascertain, from the patient, the main reason for the non-compliance, and this will be recorded as study data.

Subjects who miss doses as a result of physician-prescribed drug holidays will not be considered non-compliant. Calculation of the compliance ratio should thus be adjusted such that the "number of pills that should have been taken" reflects the drug holiday.

6.9 Agent Administration

6.9.1 Vitamin D3, 5000 IU

One half of the patients will be randomized to receive Vitamin D3 at a dose of 50,000 IU weekly for 12 weeks, followed by 2000 IU of vitamin D3 daily for 40 additional weeks. Patients will receive high dose vitamin D through the study, via 5000 IU capsules, which are available over the counter. They

will receive this study medication after all screening assessments have been completed, and eligibility has been confirmed by the study coordinator.

Patients should be carefully instructed by study personnel on how to take Vitamin D3. Patients will be instructed to take Vitamin D, 50,000 IU (10 capsules) PO on a weekly basis, on the same day each week, and at approximately the same time each dose. Vitamin D should be taken shortly after a meal. Patients may take concomitant medications along with their Vitamin D dose, provided that the medications do not interact with vitamin D absorption (e.g.cholestyramine, orlistat, phenytoin, or phenobarbital). Vitamin D3 at 50,000 IU per week will be provided for the patient by the study. This cost has been accounted for in the budget.

6.9.2 Vitamin D3, 2000 IU

After completing 12 weeks of high dose vitamin D, the patients randomized to this arm will then complete 40 additional weeks of 2000 IU daily. The pills are available in 2000 IU strength, and the patients will take 1 pill daily, with food. Again, study personnel will instruct patients on how to take vitamin D, with the same instructions and precautions provided above, in [Section 6.9.1](#).

Vitamin D3 at this dosage is available over the counter at any retail pharmacy. Patients will be provided with Schiff Vitamin D3 2000 IU Dietary Supplements, which are available at 200 pills for \$14.00. The study will cover this cost, and the research coordinator will dispense the medication at clinic visits as necessary.

6.9.3 Caltrate-D

The patients who are randomized to the standard dose Vitamin D arm will take 1 Caltrate-D pill daily. Each pill contains 600 mg of Calcium and 800 IU of Vitamin D3. Patients will be instructed to take one pill daily, with food. Again, the medicine will be provided to them by the study, at no cost to the patient. Study personnel will instruct patients on how to take vitamin D, with the same instructions and precautions provided above, in [Section 6.9.1](#).

6.9.4 Calcium, 600 mg

Patients on the high dose Vitamin D arm will be asked to take over-the-counter Calcium supplement, as is recommended as standard of care. This will not be supplied by the study, but patients will be instructed to take NatureMade Calcium 600 mg dietary supplement tablets – 1 tablet daily.

6.10 Compliance

Compliance with Vitamin D supplementation in both arms will be assessed via the research coordinator counting remaining pills in the bottle at specified visits when compliance is assessed. (Compliance with AI therapy and with vitamin D supplementation will be assessed at all the same visits). Compliance will be defined as having taken $\geq 80\%$ of expected doses of Vitamin D.

6.11 Prohibited Therapies

Patients may not take additional Calcium and Vitamin D aside from the study medications. Patients who are on cholestyramine or orlistat will not be allowed on the trial. Also, patients who are taking phenytoin or phenobarbital are not allowed on the trial either because of interaction between Vitamin D and anti-epileptic medications.

6.12 Discontinuation of Treatment

In the event that study treatment is discontinued prematurely, subjects should undergo the study procedures as described in Section 6.5. NOTE: Subjects who discontinue study therapy will still be included in the overall evaluation of response (intent-to-treat analysis), regardless of the reason for therapy discontinuation. Study treatment may be discontinued for any of the following reasons.

- Breast cancer recurrence or new breast cancer
- Failure of the subject to attend the majority of scheduled visits. The protocol chair or her designee will determine when non-compliance with clinic visits should lead to removal from study.
- Lost to follow-up
- Withdrawal of consent.
- Unacceptable major toxicity, as determined by the treating investigator.
- Intercurrent illness or condition that would, in the judgment of the treating investigator, affect assessment of clinical status to a significant degree or require discontinuation of study treatment.
- At subject's own request. Note: The reason for discontinuation from the study must be documented.

- Study is closed for any reason (e.g. new information shows that the patient's welfare would be at risk if she continued study treatment).
- General or specific changes in the participant's condition which render the participant unacceptable for further treatment in the opinion of the treating investigator physician.
- 25-hydroxyvitamin D level exceeds 120 ng/mL at any point during the study
- 25-hydroxyvitamin D level is persistently >70 ng/mL, as outlined in [Section 8.1](#).
- Corrected calcium level >11.0 mg/dL on any measurement during the study, or corrected calcium level >10.5 mg/dL on three consecutive measures, as outlined in [Section 8.1](#).
- Symptomatic hypercalcemia which warrants discontinuation, at the discretion of the treating investigator physician, with symptoms including but not limited to confusion, lethargy, constipation, nausea/vomiting, abdominal pain, or muscle weakness.
- Development of symptomatic calcium-based renal stones

6.13 Withdrawal from Study

Subjects may be withdrawn from follow-up for the following reasons:

- Subject withdraws consent for follow-up.
- Subject is lost to follow-up (after at least three documented attempts to contact her).
- Study is terminated for any reason.
- Subject death

6.14 Criteria for Removal from the Study

Participants will be removed from study when any of the criteria listed in Section 6.12 applies. All patients who are randomized in the study will be included in the overall evaluation of response (intent-to-treat analysis). All reasons for discontinuation of therapy should be documented clearly in the medical record.

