6.8 On Study Assessments and Procedures

6.8.1 Health Assessment Questionnaire

Each subject will be asked to complete the Health Assessment Questionnaire (HAQ-II) at baseline, 12 weeks, and 52 weeks. The questionnaire will be completed in the office, during the clinic visit, and it will be administered by the study coordinator. Generally, the questionnaire can be completed in less than 5 minutes by most patients. The questionnaire will be available in English, Spanish, and Vietnamese.

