8. DOSING DELAYS/DOSE MODIFICATIONS

8.1 Dose Modifications/Delays

For any patient in the study, if 25-hydroxyvitamin D level exceeds 120 ng/mL at any point, the patient will be taken off the study medication. If the 25 (OH)D level is >90 ng/mL, we will hold the vitamin D supplementation for 4 weeks, and then recheck vitamin D level. If it is <70 ng/mL after 4 weeks, the patient may resume vitamin D at 50,000 IU every other week if the patient was on the lead-in phase of the high dose arm. If the patient was on the continuation phase of the high dose arm, she would instead take 1000 IU/day. If the patient was on the standard dose arm, she would take Caltrate-D once every other day. If the 25-hydroxyvitamin D level did not fall to <70 ng/mL after 4 weeks of a drug holiday, then the vitamin D will be held for an additional 4 weeks. At the end of this 8 week period, patients will resume reduced vitamin D dosing as described above if the level has fallen to <70 ng/mL. However, if the level is still ≥70 ng/mL, then the patient will be taken off the study medication.

Similarly, if the calcium level is >11.0 mg/dL at any time during the study, the patient will be taken off the study. If the calcium level is between 10.5 and 11.0 mg/dL, the patient may follow the same vitamin D reduction schedule outlined above in which the vitamin D supplementation is held for 4 weeks, and may only be resumed at half dose if the calcium level is within normal limits, according to reference lab values. If the calcium level has not normalized after 8 weeks of drug holiday, then the patient will be taken off the study medication.

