9.4 Toxicity Management

Calcium and 25-hydroxyvitamin D levels will be followed closely while the patients are on study to avoid hypervitaminosis D. Levels of 25-hydroxyvitamin D and calcium will be monitored and managed as outlined in [Section 8.1](#). For corrected calcium level greater than 11 g/dL, management will be according to standard of care and the judgment of the treating physician. It is recommended that the patient be hydrated with one liter of IV normal saline, and given one dose of pamidronate at 90 mg IV, if renal function is within normal limits. The use of calcitonin will be at the treating

physician's discretion. The patient will be followed closely and treated until the calcium level normalizes. The patient will not be re-challenged with the study medication in this case.

If the patient develops calcium kidney stones, she will also be taken off the study. She will be referred to her primary care physician and/or urology for further management of the kidney stones.

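### Sections 6.14, 8.1 and 9.4 take a woman off the study where other sections only stop vitamin D; read literally, an early stopper who could still be measured is scored as AIA

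*Combined protocol and SAP*

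**What the plan says.** The protocol uses two different outcomes for what look like the same events.

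**Text that ends study participation**
- 6.14: "Participants will be removed from study when any of the criteria listed in Section 6.12 applies".
- 8.1, calcium: "if the calcium level is >11.0 mg/dL at any time during the study, the patient will be taken off the study".
- 9.4, stones: "If the patient develops calcium kidney stones, she will also be taken off the study".

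**Text that only stops vitamin D, or keeps follow-up going**
- 6.12, which supplies the criteria for 6.14, introduces them with "Study treatment may be discontinued for any of the following reasons". It sends early stoppers to the 6.5 visit and keeps them in the intention-to-treat evaluation.
- 8.1, vitamin D level: "if 25-hydroxyvitamin D level exceeds 120 ng/mL at any point, the patient will be taken off the study medication".
- 6.13: "Subjects may be withdrawn from follow-up for the following reasons". Four reasons follow: consent withdrawn, loss to follow-up, study termination and death. None is a laboratory or toxicity threshold.
- 6.8.1: "Each subject will be asked to complete the Health Assessment Questionnaire (HAQ-II) at baseline, 12 weeks, and 52 weeks".

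Within 6.12, the missed-visits bullet does speak of leaving the study: "The protocol chair or her designee will determine when non-compliance with clinic visits should lead to removal from study".

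Two more rules matter. Section 6.5 orders a HAQ-II for early stoppers 5 to 10 business days after therapy ends. Section 12.1.2 treats any woman who began study medication but has no 12-week HAQ as having developed AIA.

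**The concern.** One event can have two prescribed outcomes. A 25(OH)D level above 120 ng/mL means off study medication in 8.1, but it is also a 6.12 criterion, so 6.14 removes the woman from the study. With up to 5 centers, sites can reasonably act differently.

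The difference reaches the primary endpoint. On the medication-only reading, she attends at week 12 and is scored on what she reports. On the literal 6.14 reading, she has no week-12 HAQ and 12.1.2 assigns her an event. The intention-to-treat statements in 6.12 and 6.14 keep her in the denominator, but they do not secure the measurement.

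Stops for high calcium, high 25(OH)D or stones plausibly fall more on the high-dose arm, which receives 50,000 IU a week (50,000/7 = about 7,143 IU a day) against 800 IU a day. If so, the assumed events fall there too, and a real benefit becomes harder to show.

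**Working it through.** **1. Can the 6.5 HAQ stand in for week 12?** No rule says it may. Timing is also against it. After a stop on the week-4 labs, 5 to 10 business days later is about week 5 to 6. Section 1.2 gives a median onset of 1.6 months: 1.6 × 365.25/12/7 = 7.0 weeks. The substitute HAQ would usually come before that.

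**2. How wide is the route before week 12?** Section 6.2 schedules labs at week 4, and the next scheduled set is at week 12 itself. The laboratory triggers that act early are therefore mainly calcium above 11.0 mg/dL or 25(OH)D above 120 ng/mL at week 4. An 8-week hold under 8.1 that starts at week 4 ends at about week 12. Section 4.2 already excludes a history of kidney stones, baseline hypercalcemia and baseline 25(OH)D above 50 ng/mL. The documents give no removal rate, so I assume 0 to 2 women who could have been measured.

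**3. Reproduce the plan's sample size.** Inputs from 13.2: AIA rates 33% and 19%, one-sided α = 0.10, power 80%. The pooled rate is 0.26.

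n = [1.2816 × √(2 × 0.26 × 0.74) + 0.8416 × √(0.33 × 0.67 + 0.19 × 0.81)]² / 0.14² = (0.795 + 0.515)² / 0.0196 = 87.6, so 88 per group. This matches the starting figure in 13.7, which is then raised to 93.

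**4. Effect on power.** If k high-dose women are scored as AIA by rule, that arm's rate becomes p_H = [k + 0.19 × (93 − k)]/93.

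Fixed-sample power = Φ[(d − 1.2816 × SE0)/SE1], where d = 0.33 − p_H, SE0 = √(2p̄(1 − p̄)/93) with p̄ the mean of the two rates, and SE1 = √((0.33 × 0.67 + p_H(1 − p_H))/93).

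For k = 0: (0.140 − 1.2816 × 0.0643)/0.0635 = 0.906, and Φ(0.906) = 81.8%.

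With the futility look in 13.7, power = P(Z1 > 0.076 and Z2 > 1.2816). Z1 and Z2 have means θ/√2 and θ, with θ = d/SE1, and correlation √0.5. This treats the non-binding boundary as followed.

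| k (high-dose arm only) | High-dose rate | Difference (points) | Fixed-sample power | θ | Power with futility boundary |
|---|---|---|---|---|---|
| 0 | 19.0% | 14.0 | 81.8% | 2.20 | about 80% |
| 1 | 19.9% | 13.1 | 77.5% | 2.05 | about 76% |
| 2 | 20.7% | 12.3 | 72.9% | 1.90 | about 71% |

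Putting all k women in one arm is the worst case.

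**The case against.** **The natural meaning may already be off study medication.** Section 6.13 is the only list of reasons for leaving follow-up, and 6.8.1 covers every subject. Section 6.14 itself goes on to ask for the reasons for stopping therapy, as if the terms were interchangeable. The stone sentence in 9.4 directly follows one about not re-challenging with study medication. This largely stands. A reader might infer that the protocol orders the week-12 HAQ to be cancelled, but no text says so; the loss follows only from the literal reading. What remains is that 6.14 is headed as criteria for removal from the study and is worded as mandatory.

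**Scoring missing women as failures is a prespecified choice.** That stands, and 12.1.2 is not the problem. The problem is data that need not be missing.

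**The size is assumed, and its lower end is zero.** That also stands. A reader might take the 5% dropout in 13.2 as the removal rate; placed wholly in the high-dose arm, it would give 59% power. The documents do not support this. The 5% is a general dropout allowance with no split by arm, and nothing says how many of those women could still be measured at week 12.

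**Appendix B footnote 4.** A reader might add its off-trial rule for a late bone density result as another route that dilutes both arms. Section 6.1 lists that test among the screening assessments that precede randomisation, and 6.9.1 gives high-dose medication only after screening is complete. Section 12.1.2 reaches only women who began study medication. The 28-day window might run past dosing, but removals after dosing are not established.

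**Conclusion.** The conflict in wording is real and is in the current text. Its effect on the primary endpoint is conditional: it arises only if a site follows 6.14, 8.1 or 9.4 literally for a woman who has started vitamin D and stops before week 12.

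On that condition, and assuming 1 or 2 such women, all in the high-dose arm, power falls by about 4 or 9 percentage points. The number of women and their arm are both assumptions, and zero is possible.

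A reader might infer that the rule could produce a false positive. It would not: assumed events concentrated in the high-dose arm work against high-dose vitamin D. The risk is missing a real effect. Low severity, but worth correcting because the correction is cheap.

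**What to change.** Make three wording changes in one amendment.

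1. 6.14, replace the first sentence with: *Participants will be taken off study medication when a criterion in Section 6.12 applies. Unless a reason in Section 6.13 applies, or the protocol chair removes her for missed visits under 6.12, she remains on study and completes the HAQ-II and grip strength at week 12 and week 52.*
2. 8.1, calcium above 11.0 mg/dL: change *taken off the study* to *taken off the study medication*.
3. 9.4, kidney stones: make the same change.

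Leave 12.1.2 as it is, so that failure scoring still applies to women who truly cannot be measured. Leave Appendix B footnote 4 alone too: stopping vitamin D because a scan is missing would be a poor remedy.

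The cost is the amendment, plus a HAQ-II of under 5 minutes (6.8.1) and a grip test at weeks 12 and 52 for the few women who stop early. A week-52 score after breast cancer recurrence may reflect more than AIA and should be read with that in mind; the primary endpoint is at week 12.
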